### **Cohort 2: Disease-Matched Comparison Cohort (Comparison Group 1):**

1. Exposure to siponimod any time from the 4th day post the first day of LMP prior to conception up to and including end of pregnancy
2. Women with exposure to any of the following medications within 5 half-lives of conception:
  - Cladribine (Mavenclad)
  - SIP modulators
  - Teriflunomide (Aubagio)
  - Anti CD-20 monoclonal antibody

New medications (marketed after 2020) indicated for the treatment of MS will be evaluated for inclusion/exclusion criteria as the study progresses.

3. Women who have enrolled in the siponimod cohort or OMB157G2403 Kesimpta cohort with a previous pregnancy
4. Retrospective enrollment after the outcome of pregnancy is known (i.e. the pregnancy has ended prior to enrollment)
5. Results of a diagnostic test are positive for a major structural defect prior to enrollment. However, women who have had any normal or abnormal prenatal screening or diagnostic test prior to enrollment are eligible as long as the test result does not indicate a major structural defect.

### **Cohort 3: Healthy Comparison Cohort (Comparison Group 2):**

1. Exposure to Kesimpta 166 days before or to siponimod any time from the 4th day post first day of LMP prior to conception up to and including end of pregnancy
2. Women who have a diagnosis of a MS or a siponimod approved indication
3. Women who have a current diagnosis of any autoimmune disease
4. Women who have first contact with the project after prenatal diagnosis of any major structural defect
5. Women who have enrolled in the siponimod cohort or Kesimpta cohort study with a previous pregnancy
6. Women treated with Mayzent or Kesimpta for non-MS indication
7. Retrospective enrollment after the outcome of pregnancy is known (i.e. the pregnancy has ended prior to enrollment)
8. Results of a diagnostic test are positive for a major structural defect prior to enrollment. However, women who have had any normal or abnormal prenatal screening or diagnostic test prior to enrollment are eligible as long as the test result does not indicate a major structural defect.
9. Women exposed to a known human teratogen during pregnancy as confirmed by the OTIS Research Center

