#### **Cohort 1: Siponimod-Exposed Cohort**

1. Women who have enrolled in the siponimod cohort study with a previous pregnancy
2. Women who have used siponimod for an indication other than a currently approved indication
3. Women with exposure to any of the following medications within 5 half-lives prior to conception:
  - Cladribine (Mavenclad)
    - Based on the US label, animal studies indicate that there is positive evidence of teratogenicity for Cladribine
  - All other S1P modulators including fingolimod (Gilenya), ozanimod, etc.
    - S1P modulators are in the same class of drug as siponimod
  - Teriflunomide (Aubagio)
    - The teratogenicity of teriflunomide is unknown and currently under investigation
  - Other anti-CD20 monoclonal antibody: same class as Kesimpta
  - New medications (marketed after 2020) indicated for the treatment of MS will be evaluated for inclusion/exclusion criteria as the study progresses.
4. Retrospective enrollment after the outcome of pregnancy is known (i.e. the pregnancy has ended prior to enrollment)
5. Results of a diagnostic test are positive for a major structural defect prior to enrollment ([Section 7.7.2.3](#)). However, women who have had any normal or abnormal prenatal screening or diagnostic test prior to enrollment are eligible as long as the test result does not indicate a major structural defect.

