### **7.2.2.4 Analysis populations**

The Registry will collect and follow-up on reports of all types (i.e., retrospective, exposure after first trimester only, off-label indication, etc.: see [Section 7.2.2.3](#)) involving pregnancy exposure to siponimod; however, the core of the Registry will be a prospective cohort study designed to ascertain and follow-up on pregnancy exposures to siponimod and to compare these outcomes to 2 internally-generated comparison groups and one external comparison group (Metropolitan Atlanta Congenital Defects Program, or MACDP).

- Comparison Group 1 consisting of diseased-matched pregnant women who have not been exposed to siponimod at any time from the 4th day post first day of LMP prior to conception up to and including the end of current pregnancy. This will be the primary comparison group.
- Note that this cohort will be common between this study and the Kesimpta-OTIS pregnancy registry sub-study (OMB157G2403). The first 125 eligible pregnancies after OMB157G2403 protocol approval will be eligible for inclusion in both studies.
  - Comparison Group 2 consisting of pregnant women who contact the study directly or who are referred to the study, and who do not have MS, have not been exposed to a known human teratogen, and have not taken siponimod in pregnancy. This will be a secondary comparison group.
- Note that this cohort will be common between this study and the Kesimpta-OTIS pregnancy registry sub-study (OMB157G2403). The first 125 eligible pregnancies after OMB157G2403 protocol approval will be eligible for inclusion in both studies.

Based on previous OTIS experience, it is estimated that Comparison Group 2 will be similar to the exposed and primary comparison group on key demographics such as maternal age, socioeconomic status and race/ethnic distribution. However, differences between the cohorts for these demographic factors will be monitored in the annual interim reports and, should they occur, will be addressed in future recruitment efforts and in the statistical analysis phase of the study through methods such as adjustment (to be detailed in the SAP).

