Prenatal diagnostic tests prior to enrollment	Confounder	Maternal report Medical record	Tests performed prior to enrollment (Ultrasound level 1, Ultrasound level 2, Chorionic Villus Sampling, Amniocentesis).
Prenatal diagnostic tests anytime during pregnancy	Confounder	Maternal report Medical record	Tests performed anytime in pregnancy (Ultrasound level 1, Ultrasound level 2, Chorionic Villus Sampling, Amniocentesis).
Maternal pregnancy exposure to a known human teratogen	Confounder	Maternal report Medical record	Maternal pregnancy exposure to a known human teratogen (e.g., Type I diabetes) (confirm with medical record).
Years since diagnosis of approved indicated disease	Confounder	Maternal report Medical record	Years since diagnosis of approved indicated disease.
Comorbid maternal medical history	Confounder	Maternal report Medical record	Comorbid maternal medical history (e.g. chronic hypertension, asthma)
Treatment history for the indicated disease	Confounder	Maternal report Medical record	Treatment history for the indicated disease
Pregnancy complications	Covariate	Maternal report Medical record	Pregnancy complications, including infection and gestational diabetes.

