As a secondary approach, a sensitivity analysis will be considered and the following three criteria applied to identify confounders (Xu et al, 2018, Greenland et al, 1999): 1) by assessing each considered variable in a logistic regression model containing the exposure variable and the outcome variable to determine if inclusion of that single covariate changes the estimate of the odds ratio for exposure by 10% or more; 2) standardized mean differences (SMD) greater than 0.1; 3) association with the outcome with p-value < 0.2 in the unexposed cohort (comparison group 2). Care will be taken not to include those variables that are strongly associated with the exposure variable but only weakly associated with the outcome variable (e.g. instrument like variables) (Brookhart et al, 2006). The confounders identified above will be used to build the propensity score (PS) for exposure (Rosenbaum, 2002).

Balance in the covariate distributions before and after weighting will be assessed by providing the standardized mean differences of all covariates.

The primary analysis will be performed using the PS via inverse probability weighting (IPW).

As secondary analysis, the PS will be used in the so-called outcomes regression (Xu et al, 2018, Vansteelandt et al, 2014), i.e. a logistic regression model will be fitted with major structural defect (Y) as outcome, and exposure (A) and logit of propensity score (L) as regressors. In a second step, standardization will be performed to obtain the estimated causal risk ratio (Hernan and Robins, 2019). The CI for the causal risk ratio will be obtained by bootstrap.

Several sensitivity analyses will be performed for the primary outcome of major structural birth defects. One analysis will exclude those defects thought to be of chromosomal or genetic origin. Exposure to a known human teratogen is already included in the list of potential confounders for the siponimod-exposed group vs. comparison group 1. However, in the case where there are insufficient number of events to consider regression adjustment, a sensitivity analysis will be performed excluding participants with exposure to known teratogens in the siponimod-exposed group and comparison group 1 to address this potential confounder.

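### Known-teratogen exposure is excluded from the healthy cohort but not from the siponimod cohort, and 7.7.3.1.1 handles it only against comparison group 1, leaving a modest upward bias in the secondary comparison with healthy women

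*Protocol*

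**What the plan says.** **Eligibility (protocol, 7.2.2.2).** Cohort 3, exclusion 9, removes "Women exposed to a known human teratogen during pregnancy as confirmed by the OTIS Research Center". Section 7.2.2.4 describes comparison group 2 the same way, as women "who do not have MS, have not been exposed to a known human teratogen, and have not taken siponimod in pregnancy".

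For Cohort 1 the related criterion is "Women with exposure to any of the following medications within 5 half-lives prior to conception". It is followed by cladribine, other S1P modulators, teriflunomide, other anti-CD20 antibodies, and a provision to evaluate new MS drugs. There is no general known-teratogen exclusion. Cohort 2 has a similar list and no general exclusion either.

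**Variable (Table 7-1).** Teratogen exposure is collected with the role of confounder: "Maternal pregnancy exposure to a known human teratogen (e.g., Type I diabetes) (confirm with medical record". The row is not limited to any one comparison.

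**Analysis (7.7.3.1.1).** "Exposure to a known human teratogen is already included in the list of potential confounders for the siponimod-exposed group vs. comparison group 1". If events are too few for regression adjustment, the fallback is a sensitivity analysis "excluding participants with exposure to known teratogens in the siponimod-exposed group and comparison group 1 to address this potential confounder". The primary adjusted analysis is inverse probability weighting (IPW) on the propensity score (PS). The secondary one regresses the outcome on exposure and the logit of the PS, then standardizes. No trimming or overlap rule is stated.

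**Rank.** Section 6 names healthy women as the second comparator in the primary objective. Sections 7.2.2.4 and 7.7.3.1.1 make the disease-matched group the primary comparison and the healthy group a secondary one.

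**The concern.** A woman with a known teratogenic exposure outside the MS drug list can enter Cohort 1 but not Cohort 3. The protocol's own example, Type I diabetes, is such a case. Teratogen exposure raises the risk of the primary outcome, so the asymmetry pushes the siponimod-versus-healthy risk ratio in one direction only: upward.

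The usual remedy, putting the variable in the PS, does not work here. Within the Cohort 1 v Cohort 3 data every teratogen-exposed woman is a siponimod woman. Her true PS is 1, there is no healthy counterpart to weight up, and the logit of her PS is undefined.

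The protocol recognises the threat but writes the remedy for one of the two comparisons. An analysis that follows 7.7.3.1.1 literally leaves the other uncorrected. At stake is a false or exaggerated signal in a comparison named in the primary objective.

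**Working it through.** **Inputs from the protocol.** 231 live-birth pregnancies per cohort (7.5.1, Table 7-4); 3% baseline rate of major structural defects; 1:1:1 allocation; two-sided alpha 0.05 with Fisher's exact test; detectable risk ratio 3.0 at 80% power (Table 7-4).

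**Inputs assumed.** The protocol gives neither the teratogen prevalence in Cohort 1 (q) nor the teratogen risk ratio (k). Both are varied below.

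**The yardstick.** For 231 v 231 and 9% v 3%, the arcsine approximation gives 80.2% power, which reproduces the stated 80%. Exact Fisher power is 74.0%. The figure serves here only as a scale for the bias. (The text of 7.5.1 also quotes 4.4 as the detectable ratio. That needs reconciling with the table but does not affect this point.)

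**Step 1: crude bias with no siponimod effect.** The Cohort 1 rate is 3% × [(1 − q) + qk] and the Cohort 3 rate is 3%, so

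apparent RR = 1 + q(k − 1).

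Example: q = 5%, k = 3 gives 1 + 0.05 × 2 = 1.10. Extra cases are 231 × 0.03 × 0.10 = 0.69, on an expected 231 × 0.03 = 6.9.

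| q | k | Apparent RR | Extra cases per 231 | Fisher false-positive rate |
|---|---|---|---|---|
| none | – | 1.00 | 0 | 2.4% |
| 1% | 2 | 1.01 | 0.07 | 2.5% |
| 2% | 3 | 1.04 | 0.28 | 2.5% |
| 5% | 3 | 1.10 | 0.69 | 2.8% |
| 5% | 5 | 1.20 | 1.39 | 3.5% |
| 10% | 3 | 1.20 | 1.39 | 3.5% |
| 10% | 5 | 1.40 | 2.77 | 6.5% |
| 10% | 10 | 1.90 | 6.24 | 22.5% |

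**Step 2: IPW with the variable in the PS.** With equal groups, teratogen-exposed women in Cohort 1 keep weight 1 (PS = 1), while the other Cohort 1 women are weighted up to represent all unexposed-to-teratogen women in both cohorts. The weighted prevalence in the siponimod arm is therefore q/2, and it remains zero in the healthy arm:

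apparent RR ≈ 1 + (q/2)(k − 1).

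For q = 5%, k = 3 this is 1 + 0.025 × 2 = 1.05. For q = 10%, k = 5 it is 1 + 0.05 × 4 = 1.20. Large-sample limits were also computed with one ordinary confounder added (assumed prevalence 40% in Cohort 1 and 25% in the comparator, risk ratio 1.6).

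| q | k | Variable omitted, or exposed-group (ATT) weights | IPW, variable in PS | Cohort 1 restricted |
|---|---|---|---|---|
| 1% | 3 | 1.02 | 1.01 | 1.00 |
| 5% | 3 | 1.10 | 1.05 | 1.00 |
| 5% | 5 | 1.20 | 1.10 | 1.00 |
| 10% | 3 | 1.20 | 1.11 | 1.00 |
| 10% | 5 | 1.40 | 1.21 | 1.00 |

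IPW roughly halves the bias but does not remove it. Restriction removes it in every scenario.

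**Step 3: the comparison with Cohort 2.** With the exposure present in the comparator (2% assumed), the PS including the variable returns 1.00 throughout. The planned method is adequate there.

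**Step 4: which column applies.** Adjustment is planned only if there are enough events, and about 7 are expected per group with no effect. If there are too few, group 1 has the fallback exclusion, while no matching provision is written for group 2. Its crude ratio then carries the Step 1 inflation.

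**The case against.** **The SAP may deal with it.** The complete confounder list, and detail on controlling for confounders, are left to an SAP that is not shown. Restricting an analysis set for a secondary comparator could reasonably sit there. This stands in part. But the protocol is not merely silent: it names the problem and writes the remedy for group 1, and adding the variable to a list would not repair the other comparison.

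**The fallback names only the groups that have such women.** Group 2 has none to drop, and once Cohort 1 is restricted the healthy comparison is clean too. That is true of the arithmetic, but the fallback is a sensitivity analysis triggered only by too few events, and its stated purpose is the contrast with group 1.

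**A healthy reference differs in other ways.** Cohort 3 also excludes MS and any current autoimmune disease, so removing this asymmetry does not isolate a siponimod effect. This stands. Those differences, however, define the comparator; teratogen exposure does not, and it can be removed.

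**Stronger readings the documents do not support:**
- That the plan treats teratogen exposure as a confounder only for group 1. Table 7-1 lists it without that limit; only 7.7.3.1.1 narrows it.
- That no PS method could remove the bias. Trimming women with PS = 1 would, and it amounts to the restriction proposed here. The point concerns the methods as planned.
- That the primary comparison is biased. It is not, because Cohort 2 can contain teratogen-exposed women.
- That a pooled comparator (Table 7-5) fails in the same way. Pooling is conditional, and Cohort 2 can supply exposed women, so adjustment may be possible.

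**Conclusion.** The point holds for the secondary Cohort 1 v Cohort 3 comparison. Eligibility is asymmetric on a recognised cause of the primary outcome, the stated remedy covers only the other comparison, and the planned PS methods cannot balance a variable fixed at zero in one arm. The bias always raises the siponimod risk ratio.

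Its size rests on assumed values. At a prevalence of 5-10% and a teratogen risk ratio of 3-5, the ratio with no drug effect is about 1.10-1.40 crude, or 1.05-1.21 under IPW with the variable in the score. That is modest against a detectable 3.0. It vanishes if no Cohort 1 woman has such an exposure, and becomes serious only if the exposure is both common and strongly harmful (1.90 at 10% and 10). The MS drugs already excluded from Cohort 1 narrow the gap without closing it. The correction is worth making because the healthy comparison is named in the primary objective and the change is cheap.

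**What to change.** In 7.7.3.1.1, state that for every Cohort 1 v Cohort 3 comparison, Cohort 1 is restricted to women without confirmed known-teratogen exposure, using the confirmation standard already applied to Cohort 3. Make this unconditional rather than dependent on the number of events, and report the number removed.

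If the two comparators are pooled, either apply the same restriction to Cohorts 1 and 2 or adjust for the variable. Keep these women in the Cohort 1 v Cohort 2 comparison, where the variable can be balanced.

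The cost is analysis wording only, since Table 7-1 already collects the variable. The downside is that a few siponimod-exposed women leave a secondary comparison, with a small loss of precision there and a result that applies to women without such exposures.

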### **7.2.2.3 Siponimod-exposed pregnancies not eligible for the siponimod-exposed prospective cohort**

By study design, pregnancies that do not meet the exposed cohort criteria for reasons described in [Section 7.2.2.2](#) will be excluded from the cohort analysis; however, information on birth outcomes can be obtained and can be useful when reviewing the cohort data for any evidence of increased risks for the study outcomes. For this reason, women who do not meet the exposed cohort criteria will be invited to enroll in a separate exposure series. Women who are eligible for enrollment in the exposure series include the following: use of siponimod in pregnancy for an unapproved indication and retrospective reports of a siponimod-exposed pregnancy after the outcome of pregnancy is known. With informed consent, data will be collected from maternal interviews, medical records, and the dysmorphology examination using the same protocol as the cohort study to the extent possible.

### **7.2.2.4 Analysis populations**

The Registry will collect and follow-up on reports of all types (i.e., retrospective, exposure after first trimester only, off-label indication, etc.: see [Section 7.2.2.3](#)) involving pregnancy exposure to siponimod; however, the core of the Registry will be a prospective cohort study designed to ascertain and follow-up on pregnancy exposures to siponimod and to compare these outcomes to 2 internally-generated comparison groups and one external comparison group (Metropolitan Atlanta Congenital Defects Program, or MACDP).

- Comparison Group 1 consisting of diseased-matched pregnant women who have not been exposed to siponimod at any time from the 4th day post first day of LMP prior to conception up to and including the end of current pregnancy. This will be the primary comparison group.
- Note that this cohort will be common between this study and the Kesimpta-OTIS pregnancy registry sub-study (OMB157G2403). The first 125 eligible pregnancies after OMB157G2403 protocol approval will be eligible for inclusion in both studies.
  - Comparison Group 2 consisting of pregnant women who contact the study directly or who are referred to the study, and who do not have MS, have not been exposed to a known human teratogen, and have not taken siponimod in pregnancy. This will be a secondary comparison group.
- Note that this cohort will be common between this study and the Kesimpta-OTIS pregnancy registry sub-study (OMB157G2403). The first 125 eligible pregnancies after OMB157G2403 protocol approval will be eligible for inclusion in both studies.

Based on previous OTIS experience, it is estimated that Comparison Group 2 will be similar to the exposed and primary comparison group on key demographics such as maternal age, socioeconomic status and race/ethnic distribution. However, differences between the cohorts for these demographic factors will be monitored in the annual interim reports and, should they occur, will be addressed in future recruitment efforts and in the statistical analysis phase of the study through methods such as adjustment (to be detailed in the SAP).

### 7.2.2.5 Modalities of recruitment

All exposed subjects and comparison subjects will be recruited through spontaneous calls to participating OTIS member services in locations throughout North America and through active recruitment strategies, e.g., direct mailings to relevant specialists, obstetric healthcare providers, pharmacists, website, and professional meetings. Each OTIS service will provide exposure counseling in the routine manner for all exposed and unexposed women who initially make contact with the service with questions regarding a current pregnancy. Subsequently, each OTIS service will request permission to refer to the Research Center at the [REDACTED]. Potential subjects who agree to be referred will contact the Research Center or be contacted if they prefer. The OTIS member services will also refer callers to the Research Center whose exposure to siponimod does not appear to qualify for the cohort study (i.e., retrospective reports), as these will be included in the Registry Exposure Case Series. Healthcare providers can also contact the Registry and refer patients; however, in all cases the mother is the individual who provides informed consent for participation and completes the interview based data collection.

The US and Canada's siponimod package insert contains information about the siponimod pregnancy exposure registry, and encourages healthcare providers to register patients and pregnant women to register themselves by calling the study toll-free number as soon as the pregnancy is known.

In addition, members of the Scientific Advisory Board (see [Section 11.3.1](#)) will be asked to promote recruitment among colleagues. The existing Toll Free number for North American callers currently being utilized by all MotherToBaby Pregnancy Studies and the OTIS Autoimmune Diseases in Pregnancy Project [REDACTED] will be maintained as a considerable amount of previous publicity for this number will enhance ease of contact for patients to the Registry.

The existing MotherToBaby/OTIS Autoimmune Diseases in Pregnancy Project contact and referral information is available on the website and multiple methods are used to increase awareness through the website (<https://mothertobaby.org/pregnancy-studies/>), social media and print advertising. The FDA website (<http://www.fda.gov/womens/registries/default.htm>) lists the MotherToBaby/OTIS Pregnancy Studies and will have this Registry added to their listing. The study will also be listed on [ClinicalTrials.gov](http://ClinicalTrials.gov).

This information will also be made available 1) in the prescribing information (package insert) for siponimod and other product literature and promotional materials, and 2) via a link from the Novartis website. Additional venues for publicizing the Registry include: 1) linking the Registry website to other specialty provider and maternal health interest websites, 2) posting notices in appropriate journals or patient advocacy publications, and 3) later, presenting Registry data at specialty provider, and obstetrics-related scientific and clinical meetings. In addition, the Registry will enlist the aid of the U.S. FDA, the U.S. Centers for Disease Control and Prevention (CDC), and other relevant organizations in facilitating patient recruitment, and the Sponsor will also provide information about the Registry at appropriate professional meetings. Additional venues for publicizing the Registry include advocacy groups and patient support networks. The Sponsor may facilitate awareness among prescribers through Medical Science Liaisons.

The Sponsor will encourage exposed women or their Healthcare Providers to contact the Registry directly.

